**Evaluation of Omega-3 Polyunsaturated Fatty Acids Plus Low-dose
Aspirin Daily Supplementation in Surgical Therapy to Treat Generalized
Aggressive Periodontitis: Randomized Controlled Clinical Trial**

NCT03093207

May 15, 2017

Study Protocol

Periodontal destruction results mainly from the exacerbated host inflammatory response to the bacterial challenge. For this reason, research involving the modulation of host response has been developed aiming to facilitate the resolution of inflammation, as well as to promote tissue repair and periodontal stability. Recently, the use of omega-3 polyunsaturated fatty acids (Ω -3 PUFA) and low-dose acetylsalicylic acid (ASA) was related to the production of enhanced lipidic mediators and to better clinical outcomes in the treatment of chronic periodontitis. Thus, the aim of the present randomized controlled clinical trials was to evaluate the use of 900 mg Ω -3 PUFA and 100 mg ASA for 180 days as adjuvants to the treatment of generalized aggressive periodontitis (GAgP). Thirty-four GAgP patients previously submitted to NST with residual pockets were selected and underwent open flap debridement associated with Ω -3 PUFA 3 and ASA (n=17) or placebo (n=17). After 6 months, both therapies led to decreased PD ($p > 0.05$), but only the test group had CAL gain in the intergroup comparison ($p = 0,02$), as well as presented less gingival recession ($p = 0,03$), decreased dentin hypersensitivity ($p = 0,01$), lower consumption of analgesics ($p = 0,02$) and significant intragroup reduction of IL-10 ($p < 0.05$). The microbiological analysis of the residual pockets did not reveal significant changes compared to baseline. It was concluded that the proposed new therapy brought clinical benefits to the surgical treatment of GAgP patients.

Statistical Analysis Plan

Mean and standard deviation were calculated in each of the parameters. PI, BoP, PD, CAL, and GR were submitted to the Shapiro-Wilk test to evaluate the distribution of these data, and then subjected to the variance test for both intra- and intra-group comparison. In addition, the number of pockets $\geq 5\text{mm}$, the frequency of closure of these pockets, the mean reduction in PS and the gain in CAL of these pockets were assessed before and after the therapy by performing intra- and inter-group analyzes. IBM SPSS software was used to data analyses. The concentration of each cytokine/microorganism were analyzed by test of variance for intra and intergroup comparison.

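### Does it undermine the conclusion that the SAP describes no test for dentin hypersensitivity or analgesic consumption?

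*Combined protocol and SAP*

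**What the plan says.** The Study Protocol section describes 34 patients, 17 per arm, and summarises results at six months. Four clinical results have p-values below 0.05:

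- CAL gain, p = 0.02, introduced with "only the test group had CAL gain in the intergroup comparison"
- gingival recession, p = 0.03
- the other two, reported as "decreased dentin hypersensitivity ($p = 0,01$), lower consumption of analgesics ($p = 0,02".

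Pocket depth is given as p > 0.05. The laboratory result that closes the list is a "significant intragroup reduction of IL-10". The section ends: "It was concluded that the proposed new therapy brought clinical benefits to the surgical treatment of GAgP patients".

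The Statistical Analysis Plan section opens with "Mean and standard deviation were calculated in each of the parameters" and then covers three groups of variables:

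- Clinical indices: "PI, BoP, PD, CAL, and GR were submitted to the Shapiro-Wilk test", followed by a variance test.
- Pockets of 5 mm or more: their number, and "the frequency of closure of these pockets, the mean reduction in PS and the gain in CAL of these pockets were assessed", with analyses within and between groups.
- Laboratory measures: "The concentration of each cytokine/microorganism were analyzed by test of variance for intra and intergroup comparison".

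Dentin hypersensitivity and analgesic consumption are in none of the three.

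**The concern.** When a SAP assigns tests to variables by name, a reader expects every reported p-value to trace back to one of those names. Two of the four significant clinical p-values here do not, and one of them (0.01) is the smallest exact p-value in the document. Neither section gives the scale of the hypersensitivity measure, the unit of analgesic use, the period it covers, or the test applied.

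Two risks follow. First, scale, window and test might have been chosen after the data were seen; analgesic use is often skewed with many zeros, so the choice of test can matter. Second, the hypersensitivity result carries no comparison label. It stands between a CAL result marked as between groups and an IL-10 result marked as within group. If it were a within-arm change, p = 0.01 would not be evidence of a treatment difference. On the severe reading, the support for clinical benefit would shrink to CAL and recession, with the other two outcomes exploratory.

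**Working it through.** **1. Count and coverage.** Each significant clinical result in the Study Protocol section, set against the SAP:

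| Outcome | Reported p | What the SAP provides |
|---|---|---|
| CAL gain | 0.02 | Variance test for overall CAL; between-group analysis for CAL gain in pockets of 5 mm or more, no test named |
| Gingival recession | 0.03 | Variance test; the comparison is printed as intra-group twice |
| Dentin hypersensitivity | 0.01 | Not named |
| Analgesic consumption | 0.02 | Not named |

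Not covered: 2 of 4. If the within-group IL-10 result is counted too, it is 2 of 5. The omission is confirmed.

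**2. Are CAL and recession better planned?** The SAP is in the past tense throughout and shares a document with the six-month results. Nothing in it dates any of these analyses to before the data were seen. Recession appears only in the sentence that prints the intra-group term twice. That is almost certainly a slip for within and between groups, but taken literally it gives recession no between-arm test. Overall CAL depends on the same sentence. So the table shows which outcomes are described, not which were pre-specified.

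**3. Hypersensitivity, between-arm reading.** The list opens with a statement about the test group in a between-group comparison, and the within-group label appears only at IL-10. Between-arm is therefore the natural reading for the items in between, and p = 0.01 stands.

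**4. Hypersensitivity, within-arm reading.** Assume t tests on change, n = 17 per arm and equal SDs. With k the placebo change as a fraction of the test-arm change:

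- Within-arm p = 0.01 on 16 df gives t = 2.921.
- Between-arm t = 2.921 × (1 − k) / √2, on 32 df (critical value 2.037).
- k = 0: t = 2.065, p = 0.047.
- k = 0.10: t = 1.859, p = 0.072.
- k = 0.25: t = 1.549, p = 0.131.
- k = 0.50: t = 1.033, p = 0.310.
- p = 0.05 is reached at k = 1 − 2.037 × √2 / 2.921 = 0.014.

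The reported p is rounded, so the unrounded value could lie anywhere from 0.005 to 0.015:

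- Within-arm p = 0.005: t = 3.252; at k = 0 the between-arm t is 2.300 and p = 0.028; threshold k = 0.11.
- Within-arm p = 0.015: t = 2.724; at k = 0 the between-arm t is 1.926 and p = 0.063; threshold k is below zero.

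The threshold of 1.4% thus rests on decimals nobody can see, and on a t test for an outcome whose scale is not given.

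**5. Analgesics.** Any sensitivity figure needs an assumed distribution. With negative-binomial counts, 17 per arm, assumed means of 3 to 6 on placebo and 1 to 3 on test, and dispersion 0.5 to 2, consider the simulated trials in which a variance test gives p near 0.02. A rank test gives p > 0.05 in about 14% to 28% of them, so it agrees in most. Fisher's test on any use versus none gives p > 0.05 in 74% to 97%; this mainly reflects the information lost by dichotomising, and nothing in the documents suggests that analysis was used. Picking the best of the three tests raises the false-positive rate only to 6.2% to 7.5%. All of these inputs are assumptions, including use of the variance test itself.

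**The case for a change.** The strongest case for acting is that the omission is plain. The SAP is short, yet it names plaque index and covers every cytokine, while leaving out two outcomes that feed the conclusion. The opening sentence on means and standard deviations cannot produce a p-value. The variance test cannot simply be carried over, because neither scale nor unit is known. No redaction mark suggests that text was removed. Since this document already reports results, a line added now could not count as pre-planned, so an honest course might be to cite an earlier plan or call the two results exploratory.

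The first part stands in full: the SAP does not describe these two analyses, and a reader cannot reconstruct them. The last step does not. Calling two results exploratory and resting the conclusion on the other two assumes that CAL and recession were pre-specified, and the document gives no more evidence of that for them. The same caution would apply to all four. Nor does two of four measure how much the conclusion relies on these outcomes, because no primary outcome is named.

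**Conclusion.** The omission is confirmed at 2 of 4 significant clinical p-values, but it is missing detail and not a fault in a stated method. Comparing two arms of 17 on a hypersensitivity measure and on analgesic use is routine, and an analyst would choose a test to suit the scale. The documents do not show that either result is wrong. On the between-arm reading both stand as reported; the range 0.047 to 0.31 applies only on the within-arm reading of hypersensitivity with p taken as exactly 0.01, and the analgesic figures only under assumed distributions. The doubled intra-group wording is a clerical slip.

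This rests on two judgements: that the hypersensitivity p-value compares the arms, and that the past-tense SAP supports no split between planned and unplanned outcomes. If the hypersensitivity result proved to be within-arm, that one result would no longer count as evidence of a treatment difference on its own; the reported CAL, recession and analgesic results would be unaffected. Scale, window, test and comparison label belong in the report of results, and no change to the plan is called for.

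### Does the IL-10 result, reported only as a within-arm change, call for a change to the plan?

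*Combined protocol and SAP*

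**What the plan says.** The Study Protocol section of the combined document describes 34 patients, 17 per arm, who "were selected and underwent open flap debridement associated with" either the supplement or placebo. Its results sentence first says that at 6 months "both therapies led to decreased PD". It then turns to the contrast between arms, "but only the test group had CAL gain in the intergroup comparison", and goes on to recession, hypersensitivity and analgesic use. The last item is a "significant intragroup reduction of IL-10", with p < 0.05. Neither the IL-10 change on placebo nor a between-arm IL-10 result is printed.

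The Statistical Analysis Plan section says that concentrations of each cytokine and microorganism "were analyzed by test of variance for intra and intergroup comparison". IL-10 is not named there, but it is covered as one of the cytokines.

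The closing sentence of the Study Protocol section reads: "It was concluded that the proposed new therapy brought clinical benefits". It does not cite IL-10.

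**The concern.** The sentence moves from a between-arm result (CAL) to a within-arm result (IL-10) under one opening that singles out the test group. A quick reader may take the IL-10 fall as one more difference from placebo. That does not follow. Both arms had surgery, so a change within the test arm mixes surgery, time and supplement, and only the randomised contrast separates them. At most, the word only implies that the placebo change was not significant, and a significant result beside a non-significant one is not a test of their difference.

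The section gives modulation of the host response as its rationale, and IL-10 is the only cytokine result printed. It could therefore be taken as mechanistic support. If the between-arm comparison had not been planned, or if the conclusion leaned on IL-10, an analysis would have to be added or a claim withdrawn.

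**Working it through.** **No figure to reproduce.** The documents give no IL-10 mean, SD, exact p-value, placebo change or number of usable samples, and no significance level. The arm size of 17 comes from the Study Protocol section. Everything else here is assumed: two-sided 0.05, normal data, all 17 pairs usable in each arm, equal SDs of change, and independent arms.

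**From within-arm to between-arm p.** Let t_w be the paired t in the test arm (16 df), and let k be the placebo change as a fraction of the test-arm change. A positive k is a fall and a negative k a rise. Then

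t_b = t_w × (1 − k) / √2, on 32 df.

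A within-arm p of exactly 0.05 means t_w = 2.120, so with k = 0, t_b = 2.120 / 1.414 = 1.499 and p = 0.144. A two-arm, two-visit analysis of variance gives the same answer, since its group-by-time F(1,32) is 1.499² = 2.247.

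| Within-arm p | Placebo unchanged (k = 0) | Placebo fell half as much (k = 0.5) |
|---|---|---|
| 0.05 | 0.144 | 0.459 |
| 0.01 | 0.047 | 0.310 |
| 0.001 | 0.008 | 0.165 |

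Nothing in the documents excludes a rise on placebo. At a within-arm p of 0.05, k = −0.5 gives t_b = 1.499 × 1.5 = 2.249 and p = 0.032. With k = −1, t_b = 1.499 × 2 = 2.998 and p is about 0.005.

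**Other forms of the between-arm test.** If the arms are compared on 6-month concentrations, with equal baselines and no placebo change, then t_b = 1.499 × √(2(1 − r)), where r is the correlation between baseline and 6 months. For r = 0, 0.3, 0.5 and 0.7, p = 0.042, 0.086, 0.144 and 0.254. With 10, 12 or 15 usable pairs per arm, change scores and k = 0, a within-arm p of 0.05 gives 0.127, 0.134 or 0.141.

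**How often only the test arm would show a significant fall.** Suppose both arms have the same true fall, and let u be the one-direction power of the paired test. The chance is u(1 − u):

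- no true change: 0.025 × 0.975 = 0.024
- 0.3 SD: 0.168
- 0.5 SD: 0.491 × 0.509 = 0.250
- 1.0 SD: 0.028

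The pattern is common only if surgery itself moves IL-10 by a moderate amount. The documents do not show that it does: the shared improvement they report is in PD, a different outcome.

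**Side by side.** The summary prints the within-arm half of the cytokine analysis. The Statistical Analysis Plan names both halves. The conclusion uses neither.

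**The case for a change.** The best case for action is that an honest label does not supply the missing result. The list is grammatically continuous and opens with a between-arm finding. IL-10 is the only cytokine reported, and the between-arm p-value would have taken one more clause. Choosing to print the within-arm p-value tilts the reading towards a supplement effect. If the word only is read as not reaching IL-10, the sentence says even less about the arms.

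Part of this stands. As printed, the IL-10 statement is not evidence of a supplement effect, and the summary would be clearer with the between-arm result and placebo values beside it, or with the within-arm result marked as descriptive.

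The rest does not carry. One sentence uses the between-arm label for CAL and the within-arm label for IL-10, so the distinction is in plain view. No sentence credits the IL-10 fall to the supplement. The clinical results also appear without means, SDs or intervals, so the missing IL-10 detail fits the brevity of an abstract-style paragraph. Whether the between-arm result is reported elsewhere cannot be seen from these documents.

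**Conclusion.** No change to the plan. The omission is real, but it lies in a one-paragraph summary. The planned analysis already includes the between-arm cytokine comparison, so adding the result to the summary would alter no design feature, no analysis and no stated conclusion.

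Its reach is limited to how the IL-10 statement is read. Under the assumptions above, a within-arm p of 0.05 is compatible with a between-arm p from about 0.005 (placebo rose as much as the test arm fell) to 0.459 (placebo fell half as much), and a placebo fall closer to the test-arm fall would take it higher. The printed p-value therefore neither shows nor excludes a difference between arms. These values illustrate what the p-value leaves open and do not reconstruct the trial's IL-10 data. The conclusion on clinical benefits is unaffected.

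### The between-arm variance test is undefined and uses no baseline covariate; a post hoc ANCOVA on baseline, shown beside the reported analysis, would usually be more precise with 17 per arm

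*Combined protocol and SAP*

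**What the plan says.** The Statistical Analysis Plan is one paragraph. After a Shapiro-Wilk test, PI, BoP, PD, CAL and GR were "then subjected to the variance test for both intra- and intra-group comparison". The second *intra* is presumably meant to be *inter*. The sentence on laboratory outcomes supports that reading: "The concentration of each cytokine/microorganism were analyzed by test of variance for intra and intergroup comparison". So does the Study Protocol section, which prints between-arm p-values. No response variable, model terms or covariate are given for either group of outcomes.

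Baseline values exist. The outcomes in pockets of 5 mm or more "were assessed before and after the therapy by performing intra- and inter-group analyzes", and the Study Protocol section says that the microbiology "did not reveal significant changes compared to baseline". Within-group testing of the clinical parameters needs a baseline value as well. The plan uses baseline only by subtraction (reduction, gain) or in within-group tests.

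The Study Protocol section reports 17 patients per arm. At 6 months "only the test group had CAL gain in the intergroup comparison" (p = 0.02), and the test group is described "as well as presented less gingival recession" (p = 0.03).

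**The concern.** The wording fits an ANOVA on 6-month values alone. It also fits a change-score ANOVA or, equivalently at two visits, the group-by-time term of a repeated-measures ANOVA. The references to CAL gain point towards change for CAL at least, but the plan does not settle it, and for GR there is no hint. These tests can give different p-values on the same data, so the reported results cannot be reproduced from the plan.

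Both readings also treat the baseline slope as known: zero for the 6-month comparison, one for the change score. ANCOVA estimates it, which usually gives a smaller standard error. That matters with 34 patients and a favourable conclusion that rests partly on p = 0.02 and p = 0.03.

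**Working it through.** The documents give no SD, correlation, effect size, alpha or power calculation, so there is no stated figure to reproduce. The check asks how far the three analyses differ at this sample size.

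**Inputs.** From the Study Protocol section: N = 34, 17 per arm, p = 0.02 (CAL), p = 0.03 (GR). Assumed: one value per patient, equal SD at both visits, baseline/6-month correlation r from 0.3 to 0.8, true difference 0.8 SD of the 6-month value, two-sided 5% level.

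**Relative variance of the arm difference.**
- 6-month value only: 1
- Change score: 2(1 − r)
- ANCOVA: (1 − r²) × 31/30, where 31/30 = (N − 3)/(N − 4) = 1.033 is the cost of estimating the slope

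Hence ANCOVA / 6-month only = 1.033(1 − r²), and ANCOVA / change = 1.033(1 + r)/2.

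| r | Variance v 6-month only | Variance v change | Power: ANCOVA / change / 6-month only |
|---|---|---|---|
| 0.3 | 0.940 | 0.672 | 64 / 48 / 62% |
| 0.5 | 0.775 | 0.775 | 73 / 62 / 62% |
| 0.6 | 0.661 | 0.827 | 79 / 72 / 62% |
| 0.8 | 0.372 | 0.930 | 96 / 95 / 62% |

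Power is from the noncentral t (32 df; 31 df for ANCOVA). Simulation of 20,000 trials per r gave 64.0, 72.7, 79.6 and 96.0% for ANCOVA, with type I error of 4.8–5.2% for all three methods. At r = 0.5, 17/0.775 ≈ 22 per arm.

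**Break-even.** ANCOVA loses to the 6-month comparison if |r| < √(1 − 1/1.033) = 0.18, and to the change score if r > 2/1.033 − 1 = 0.94. The loss there is under 2% of the standard error.

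**Effects implied by the printed p-values**, if they come from a two-group test with 32 df: t = 2.449 and 2.271. Multiplying by √(2/17) = 0.343 gives 0.840 and 0.779 SD of whichever variable was analysed.

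**How far those p-values could move.** Take r = 0.5, where the two readings give the same numbers, a within-arm SD of 1, and a chance baseline difference of one standard error (0.343 SD).
- Adjusted estimate = 0.840 ∓ 0.5 × 0.343 = 0.668 or 1.011 (CAL); 0.779 ∓ 0.5 × 0.343 = 0.608 or 0.951 (GR)
- SE = √(0.75 × 32/31 × (2/17 + 0.343²/32)) = 0.3065, 31 df
- CAL: t = 2.18 or 3.30, p = 0.037 or 0.002
- GR: t = 1.98 or 3.10, p = 0.056 or 0.004

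With no baseline difference the SE is √(0.75 × 32/31 × 2/17) = 0.3018, and p becomes 0.009 (CAL) and 0.015 (GR).

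**The case against.** The strongest reply is that two points of unequal weight are joined here. The undefined test is a plain reporting gap, whereas the absence of ANCOVA is a choice among valid methods. Results are already reported, so extra precision cannot change the design, and the added analysis can only be supportive. That is fair. It limits the remedy to a labelled post hoc analysis, but such an analysis is nearly free on data already in hand.

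The size rests on an r that the documents do not give, and r = 0.5 is about where the gain peaks. The single 0.8 SD also mixes scales: if CAL was analysed as change, 0.84 SD of change is 0.84 × √(2(1 − r)) SD of the 6-month value, or 0.99 at r = 0.3 and 0.53 at r = 0.8. These points stand, so the power column is illustrative. The variance ratios do not depend on the effect size.

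The p-value illustration does not overturn the conclusions. CAL stays below 0.05 in every case shown. GR reaches 0.056 only with an adverse baseline imbalance that the documents do not report, and at r = 0.7 under the 6-month reading it would be 0.041.

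Finally, the readings considered may be incomplete. The plan does not state the unit of analysis or the number of visits, and a repeated-measures ANOVA might have tested an arm effect averaged over visits. That reading would be less powerful still, and it underlines the need to define the test.

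**Conclusion.** The concern holds. That the test and its response are undefined, and that no baseline covariate is named, is plain from the text, apart from reading the printed *intra- and intra-group* as a slip. The precision claim holds for correlations between about 0.18 and 0.94, assuming equal SDs at both visits and one value per patient. Across r = 0.3 to 0.8, ANCOVA removes 6% to 63% of the variance of a 6-month comparison and 33% to 7% of that of a change score. Against the better of the two, the power gain at 0.8 SD is 1 to 11 points. Confidence in the size is medium because r is unknown. The issue is definition and precision, and it does not show that the reported CAL and GR findings are wrong.

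**What to change.** 1. State which test was run for each outcome, on which response (6-month value or change), at which visits and on what unit. Correct the *intra- and intra-group* wording.
2. For PI, BoP, PD, CAL, GR and the continuous pocket outcomes (patient-level mean PS reduction and CAL gain in pockets of 5 mm or more), add an ANCOVA with the 6-month patient-level value as response, arm as factor and that outcome's baseline as covariate. Report the adjusted difference with its 95% CI. Using gain as the response with the same baseline covariate gives the same arm difference.
3. Extend it to cytokines and microorganisms only on a transformed scale, with a stated rule for zero or undetectable values. It does not apply to pocket closure or analgesic use.
4. Show the ANCOVA beside the original analysis, labelled post hoc, without replacing the reported p-values.

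The cost is a few sentences of SAP text, a standard SPSS procedure, one degree of freedom per model (31 instead of 32) and an assumed roughly linear relation to baseline. The sponsor should accept in advance that the p-values may move either way.

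### Within-arm before/after tests in pockets selected at 5 mm or more are open to regression to the mean; the between-arm comparison is not

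*Combined protocol and SAP*

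**What the plan says.** The Statistical Analysis Plan first lists PD, CAL and other clinical parameters for an analysis of variance. It then turns to a subset of sites. The outcomes begin with "the number of pockets $\geq 5\text{mm}$, the frequency of closure of these pockets" and go on to mean reduction in PS (apparently probing depth) and CAL gain in the same pockets. All of these "were assessed before and after the therapy by performing intra- and inter-group analyzes". One sentence therefore plans both a within-arm and a between-arm analysis of pockets defined by a depth threshold.

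On the patients, the Study Protocol says: "Thirty-four GAgP patients previously submitted to NST with residual pockets were selected". Both arms, 17 patients each, had open flap debridement, with the supplement and aspirin in one arm and placebo in the other.

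The documents do not say whether the reading that classifies a pocket as 5 mm or more is also its before value. They do not define closure, and they mention no replicate reading, examiner-error figure or allowance for regression to the mean.

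**The concern.** A recorded depth is the true depth plus probing error. Sites kept because the recorded value reached 5 mm include too many whose error was positive. At the next visit the error is drawn afresh, so the average reading falls even if nothing has changed. If the selecting reading also serves as baseline, that fall counts as PD reduction, and some sites cross back under 5 mm and count as closed. CAL is not the selecting measure, but when it is taken at the same probing it shares part of the error, so CAL gain is affected in the same direction.

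At stake is the meaning of the within-arm tests. A significant reduction or a non-zero closure rate in either arm could not be taken as evidence that the therapy worked, because the test cannot separate the artefact from a real effect of the surgery that both arms received.

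**Working it through.** **The plan's own figure.** There is none to reproduce: the documents give no SD, probing error, effect size or sample-size derivation.

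**Inputs from the documents.** Threshold 5 mm; 17 patients per arm; the same pocket outcomes analysed within and between arms.

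**Assumed inputs (not in the documents).** Mean true PD 3.5 mm; between-site SD 1.0 or 1.5 mm; probing-error SD 0.3, 0.5 or 0.8 mm. For the simulation also: 120 sites per patient, between-patient SD 0.5 mm, readings rounded to whole mm. True change is zero throughout.

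**Step 1: closed form.** For sites selected above a cut-off c, with true mean μ, site SD σ and error SD e:

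s = √(σ² + e²), z = (c − μ)/s, expected fall = (e²/s) × φ(z)/(1 − Φ(z)).

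Worked case with σ = 1.0, e = 0.5, c = 4.5 (where a whole-mm reading rounds up to 5): s = √1.25 = 1.118; z = 1.0/1.118 = 0.894; φ(z) = 0.267; 1 − Φ(z) = 0.186; fall = (0.25/1.118) × (0.267/0.186) ≈ 0.32 mm.

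Over the assumed values the range is 0.07 mm (σ = 1.5, e = 0.3, c = 4.5) to 0.83 mm (σ = 1.0, e = 0.8, c = 5).

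**Step 2: simulation.** 17 versus 17 patients, 1,000 runs per setting. Each patient's mean change in the selected pockets was tested within one arm (one-sample t-test) and between arms (two-sample t-test) at 5%. Selection and baseline used the same reading.

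| Site SD | Error SD | Spurious PD reduction (mm) | Closed below 5 mm | Closed to 3 mm or less | Within-arm rejection | Between-arm rejection |
|---|---|---|---|---|---|---|
| 1.0 | 0.3 | 0.25 | 20.9% | 0.2% | 99.5% | 5.1% |
| 1.0 | 0.5 | 0.43 | 32.1% | 3.8% | 100% | 5.4% |
| 1.0 | 0.8 | 0.77 | 43.8% | 14.3% | 100% | 4.8% |
| 1.5 | 0.3 | 0.14 | 13.0% | 0.1% | 99.9% | 5.8% |
| 1.5 | 0.5 | 0.26 | 20.9% | 2.2% | 100% | 4.5% |
| 1.5 | 0.8 | 0.52 | 30.6% | 9.1% | 100% | 4.3% |

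The mean arm difference was 0.00 to 0.01 mm in absolute value. With 1,000 runs the simulation error on a 5% rate is √(0.05 × 0.95/1000) = 0.7 percentage points, so the between-arm rates agree with 5%.

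**Step 3: separate readings.** With error SD 0.5 mm, selecting on one reading and taking baseline from another gave a mean change of 0.00 mm and within-arm rejection of 4.3% and 5.8%. The artefact comes from the double use of one reading.

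**Step 4: the count.** Counting all sites at 5 mm or more afresh at each visit gave a change of about 0.01 to 0.05 sites per patient, essentially none.

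**Step 5: other assumptions.** With true mean 3.5 or 4.0 mm, site SD 1.3 mm, error SD 0.4 to 0.8 mm and 2,000,000 sites per setting, the spurious reduction was 0.19 to 0.60 mm and closure below 5 mm 17% to 38%, inside the ranges above. No magnitude was computed for CAL.

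**The case against.** The strongest reply is that the trial's question is unaffected. The regimen is tested as an adjunct against placebo, with surgery in both arms, and the same sentence plans the between-arm comparison. This stands: the artefact is equal in expectation in the two arms and cancels. A valid between-arm test does not, however, repair the within-arm test planned beside it.

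The double use of one reading is inferred, not stated. That also stands, and a separate baseline reading would remove the problem. But none is described, and a before/after analysis of the pockets so identified most naturally uses one baseline charting.

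A reader might go further and infer that the Study Protocol's "After 6 months, both therapies led to decreased PD" rests on this artefact. The documents do not support that. The statement carries p > 0.05, it does not refer to pockets of 5 mm or more, and the plan analyses PD separately from the pocket outcomes. The CAL result is described as an intergroup one, and no closure result is reported there. Nor can the whole pocket analysis be called invalid: the between-arm part is sound in this respect, and the count is not affected if taken over all sites at each visit.

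Finally, the magnitude is assumption throughout, and zero change is unlikely within an arm that had surgery. The share of any observed change due to the artefact therefore cannot be determined. The direction is clear once the same reading is used twice; the size is not.

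**Conclusion.** The point holds in limited form. As written, the plan includes within-arm tests of PD reduction, closure and CAL gain in threshold-selected pockets. Provided the qualifying reading is also the baseline, these tests are biased toward improvement in both arms. The ranges of 0.14 to 0.77 mm and 13% to 44% rest on the assumed depth distribution, error SDs and whole-mm readings. The closure range also assumes that closure means falling below 5 mm; if it means 3 mm or less, the range is about 0.1% to 14%. Near-certain within-arm significance under no change depends on the assumed number of sites too.

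The test-versus-placebo inference is untouched. This is a weakness in a secondary use of the data that should be corrected, and it gives no reason to doubt the randomised comparison.

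**What to change.** In the pocket sentence of the Statistical Analysis Plan:

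- Compute one value per patient for each outcome: the proportion of baseline pockets of 5 mm or more that closed, and the mean PD change and mean CAL change in those pockets.
- Base inference only on the between-arm difference in these values, with a 95% CI.
- Report within-arm pocket change descriptively, without p-values and with a note on regression to the mean.
- Define closure, and state whether the qualifying and baseline readings are separate.

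Apply the same caveat to within-arm change in full-mouth means. They avoid site selection, but patients were themselves selected for residual pockets, so such means reduce the artefact without removing it.

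The cost is a change of wording and a patient-level re-analysis of existing data. The within-arm p-values for these pockets are lost.
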